1.2.2 Nonclinical Experience with GDC-0853

GDC-0853 is a highly selective, orally administered, reversible inhibitor of BTK that is being developed by Genentech, Inc. as a potential therapeutic for autoimmune diseases,

including rheumatoid arthritis (RA) and SLE. GDC-0853 has undergone extensive investigation in nonclinical in vitro and in vivo studies to characterize its pharmacological, metabolic, and toxicological properties (see the GDC-0853 Investigator's Brochure).

In vitro cell-based experiments suggest that antagonism of BTK leads to inhibition of BCR-dependent cell proliferation and a reduction of inflammatory cytokine production from myeloid cells (including tumor necrosis factor-alpha [TNF- α], interleukin [IL]-1, and IL-6) by preventing signaling through the Fc γ RIII receptor (di Paolo et al. 2011; Liu et al. 2011). GDC-0853 effectively blocks BCR- and CD40-mediated activation and proliferation of B cells. BTK in B cells also plays a role in toll-like receptor (TLR) 4-mediated B-cell proliferation and class switching. In monocytes, GDC-0853 inhibits TLR4- and immune complex-mediated inflammatory cytokine production, including TNF- α , which contributes to disease pathogenesis in SLE (Mina-Osorio et al. 2013; Bender et al. 2016). In dendritic cells, BTK contributes to TLR8-mediated cytokine production (TNF- α and IL-6) (Sochorová et al. 2007). In basophils, BTK-dependent activation of the Fc epsilon receptor leads to activation and upregulation of CD63. In addition, GDC-0853 has been shown to inhibit the differentiation of human plasmablasts into plasma cells in vitro (see the GDC-0853 Investigator's Brochure). Patients with lupus have multiple abnormalities in the blood, including increased levels of plasmablasts (Anolik et al. 2004). Together, these data suggest that lupus patients with elevated levels of plasmablasts might demonstrate a more robust clinical response to GDC-0853. Therefore, an RNA signature biomarker encompassing genes preferentially expressed in plasmablasts was developed to detect the presence of elevated plasmablasts in the peripheral blood. In addition, efficacy in patients with high or low levels of the plasmablast signature will be compared for potential increased or decreased efficacy, respectively (see the GDC-0853 Investigator's Brochure).

The efficacy of GDC-0853 has been investigated in inflammatory models of arthritis as well as immune-complex mediated renal-injury models similar to the manifestations of human SLE. Arthritis was investigated in female Lewis rats with developing type II collagen-induced arthritis (CIA). GDC-0853 treatment was well tolerated and resulted in significant and dose-dependent reduction in ankle swelling. GDC-0853 was effective at significantly reducing anti-rat collagen II IgG antibodies in the serum (obtained on Day 16) with daily (QD) doses ≥ 0.25 mg/kg/day. However, there was no effect of GDC-0853 treatment on total anti-rat IgG antibodies in the serum. Findings from the histopathology evaluation were consistent with the clinical findings. Immune-complex mediated inflammation (induced by autoantibodies) and tissue injury is central to the pathogenesis and the majority of clinical manifestations of SLE. GDC-0853 in nonclinical studies is a potent inhibitor of these processes. Studies in interferon (IFN)-alpha-accelerated, New Zealand Black (NZB)/New Zealand White (NZW), lupus-prone mice have shown that BTK-inhibition resulted in dose-dependent improvement in survival (see the GDC-0853 Investigator's Brochure). In addition, BTK inhibition reduces the development and levels of splenic plasmablasts, a pool of

activated antibody-producing B cells, and systemic inflammation as evidenced by a decrease in the type-1 IFN signature in peripheral blood mononuclear cells.

The GDC-0853 safety profile has been assessed in repeat-dose, general toxicology studies (daily oral dosing) ranging from 1 week to 9 months in rats and dogs; in vitro and in vivo genetic toxicology studies; in vitro phototoxicity evaluation; in vitro and in vivo safety pharmacology studies of the central nervous, respiratory, and cardiovascular systems; and embryo-fetal development (Seg II) studies in rats and rabbits. Overall, GDC-0853 was well tolerated for 6 months in rats (up to 104 $\mu\text{M}\cdot\text{hr}$) and 9 months in dogs (up to 36 $\mu\text{M}\cdot\text{hr}$). Notable findings identified in nonclinical toxicology studies include vascular inflammation in dogs ($\geq 56 \mu\text{M}\cdot\text{hr}$), hepatotoxicity in dogs (180 $\mu\text{M}\cdot\text{hr}$), and a minimal increase in corrected QT (QTc) interval in dogs (7 msec or 3%; extrapolated unbound maximum observed concentration [C_{max}] of 3.17 μM). Fetal malformations in rats (627 $\mu\text{M}\cdot\text{hr}$) and rabbits ($\geq 10.6 \mu\text{M}\cdot\text{hr}$) warrant the continued use of contraception in clinical trials. On the basis of the nonclinical and clinical safety data to date, GDC-0853 is expected to be well tolerated at the doses and duration administered in the parent Study GA30044 and the current study (GA30066).

1.2.3 Clinical Experience with GDC-0853

As of 10 May 2017, GDC-0853 or placebo has been administered to 406 subjects (i.e., 203 healthy subjects, 24 patients with hematological malignancies, 172 patients with RA, and 7 patients with SLE) at doses ranging from 0.5 to 600 mg and has been well tolerated with no safety signals. In the single-ascending dose (SAD; GP29318), multiple-ascending dose (MAD; GA29347), relative bioavailability (GP29832), and oncology (GO29089) studies, GDC-0853 was generally well tolerated with adverse events being mostly non-serious, mild, and self-limited and with no dose-limiting adverse events (DLAEs) or dose-limiting toxicities.

In the SAD and MAD healthy volunteer studies, there were no DLAEs, serious adverse events, or concerning patterns of adverse events that would preclude further development of GDC-0853. Adverse events in healthy volunteers were all mild and included skin reactions (rash, contact dermatitis, and skin irritation from ECG leads; 1 subject each), nausea (2 subjects), headache, toothache, contusion, and asymptomatic bacteriuria (1 subject each).

In patients with hematological malignancies, the majority of adverse events were National Cancer Institute Common Terminology Criteria for Adverse Events (NCI CTCAE) Grade 1 or Grade 2 and included fatigue, nausea, diarrhea, headache, abdominal pain, dizziness, cough, and thrombocytopenia. There were 9 serious adverse events reported in 5 patients: abdominal pain, lung infiltration, lung infection and pneumonia, febrile neutropenia, gastrointestinal (GI) hemorrhage and upper GI hemorrhage, and H1N1 influenza and influenza pneumonia. There were 2 deaths during the study due to complications of confirmed influenza (H1N1 influenza and influenza pneumonia). As of May 2017, 6 patients remain on GDC-0853 (400 mg QD) in

Study GO29089 with daily dosing lasting up to 23 months (range 18–23, average 21 months).

GDC-0853 is also being investigated in two ongoing Phase II trials in RA (blinded, placebo-controlled Study GA29350 and open-label extension [OLE] Study GA30067) and in SLE (blinded, placebo-controlled Study GA30044). As of 10 May 2017, 172 patients with RA had received GDC-0853/placebo in Study GA29350; 53 of these patients have entered Study GA30067 and received open-label GDC-0853. An additional 7 patients with SLE have received GDC-0853/placebo in Study GA30044. Reported adverse events in the three trials have been mostly non-serious, mild, and self-limiting. In the blinded trials, there has been one reported severe adverse event (infection) and two Grade 3 adverse events (elevations in ALT/AST).

Refer to the GDC-0853 Investigator's Brochure for additional details on clinical studies.

1.3 STUDY RATIONALE AND BENEFIT–RISK ASSESSMENT

The results from the Phase I studies, nonclinical toxicology studies, and studies in a nonclinical model of SLE support further evaluation of GDC-0853 as a potential treatment for SLE. The goal of the parent Phase II study (GA30044) is to evaluate the safety and efficacy of GDC-0853 in combination with standard of care (SOC) in patients with moderate to severe SLE. The study tests two dose levels of GDC-0853 in comparison with placebo when added to background SOC. The study was powered to detect a meaningful clinical benefit in a composite measure of disease activity across multiple organ systems (see Section 3.3.4.1) and includes multiple safety assessments and monitoring by an unblinded Internal Monitoring Committee (IMC) and a Scientific Oversight Committee.

This OLE Study GA30066 will evaluate the long-term safety and efficacy of GDC-0853 in patients with SLE who have completed the ongoing, blinded Phase II Study GA30044. In this study, all patients will receive GDC-0853 starting at a dose of 200 mg twice a day (BID) for up to 48 weeks of treatment. Patients will be allowed to continue and adjust their background SOC therapy.

Inhibition of BTK offers a promising mechanism for the treatment of autoimmune diseases, such as RA and SLE (see the GDC-0853 Investigator's Brochure); however, data from clinical studies are lacking. Humans with a mutation in the XLA gene and who, therefore, lack functional BTK from birth, can live relatively normal lives on a standard therapy of IV Ig (Kaveri et al. 2011), suggesting that BTK can be safely inhibited, especially in people with established immune systems. GDC-0853 did not deplete IgG substantially during short-term treatment of healthy subjects in Phase I studies (see GDC-0853 Investigator's Brochure), but it is not known whether long-term treatment of patients will induce depletion. Therefore, IgG levels will be carefully monitored in this study. Clinical data to date suggest that IgG levels in patients with an established

immune system may not be significantly depleted, perhaps because BTK inhibitors target only the kinase domain and other BTK activities remain intact (Byrd et al. 2013).

Overall, GDC-0853 has been well tolerated in Phase I healthy subjects and oncology studies. Ongoing clinical studies include Phase II studies in SLE (GA30044), RA (GA29350 and GA30067), and chronic spontaneous urticaria (GS39684), as well as clinical pharmacology studies in healthy volunteers. Based on the compelling mechanism for BTK inhibition in SLE and the promising results in NZB/NZW lupus-prone mice, the benefit–risk ratio for this study is considered appropriate (see the GDC-0853 Investigator’s Brochure). The safety profile of GDC-0853 will be further characterized in this Phase II study. A robust safety-monitoring plan that describes the potential risks for GDC-0853 and the risk-mitigation strategies to minimize risks for the patients in this trial are provided in Section 5.1.

Clinical experience with GDC-0853 to date has not generated safety concerns that would preclude further evaluation in patients with autoimmune diseases (see the GDC-0853 Investigator’s Brochure).

1.3.1 Primary Nonclinical Toxicity Findings

The no observed adverse effect levels (NOAELs) determined in the repeat-dose, 6-month Wistar Han rat (20 mg/kg; 104 $\mu\text{M}\cdot\text{hr}$) and 9-month dog (10 mg/kg; 36 $\mu\text{M}\cdot\text{hr}$) studies support multiple-dose exposures in SLE patients at the proposed clinical doses,

[REDACTED]. The primary toxicities identified in animals include the following (see Section 1.2.2 and the GDC-0853 Investigator’s Brochure for details):

- Vascular inflammation in dogs, characterized by endothelial necrosis, proliferation and hypertrophy, vascular/perivascular lymphocyte and macrophage infiltrates, and occasional necrosis of the medial smooth-muscle cells were observed in a 4-week toxicity study at $\geq 56 \mu\text{M}\cdot\text{hr}$, and these changes were not completely reversed by the end of the 4-week recovery period. However, in the 9-month toxicity study in dogs, no GDC-0853-related vascular inflammation was observed up to the highest dose of 10 mg/kg/day (36 $\mu\text{M}\cdot\text{hr}$). [REDACTED]
- Effects on lymphocytes and Igs in rats and dogs were reversible and considered to be related to pharmacological activity involving BTK inhibition. In rats, after 4 weeks of dosing, elevated circulating total lymphocyte counts were observed at $\geq 20 \text{ mg/kg/day}$ ($\geq 104 \mu\text{M}\cdot\text{hr}$). In dogs, after 4 months dosing, decreased circulating total lymphocytes were observed at $\geq 10 \text{ mg/kg/day}$ ($\geq 36 \mu\text{M}\cdot\text{hr}$). Peripheral blood immunophenotyping showed decreased circulating B-cell counts in male rats at 20 mg/kg/day and in dogs at $\geq 1 \text{ mg/kg/day}$ ($\geq 2.1 \mu\text{M}\cdot\text{hr}$); there were no GDC-0853–related effects on total T, helper T, or cytotoxic T cells. Ig isotyping in high-dose dogs (36 $\mu\text{M}\cdot\text{hr}$) and rats (104 $\mu\text{M}\cdot\text{hr}$) showed decreased IgG

concentration; mid- and high-dose rats ($\geq 17 \mu\text{M}\cdot\text{hr}$) also had decreased IgM. Histopathology in rats and dogs showed a decrease in the number of lymphocytes in follicular germinal centers in the spleen, mesenteric and mandibular lymph nodes, and/or Peyer's patches.

- Minimal to marked, dose-dependent increases in ALT, AST, and/or bilirubin have been observed in rats administered $\geq 6 \text{ mg/kg/day}$ ($\geq 17 \mu\text{M}\cdot\text{hr}$). Hepatotoxicity in dogs, consisting of increases in ALT, AST, ALP, gamma-glutamyl transpeptidase (GGT), and/or total bilirubin levels correlated with microscopic findings of minimal hepatocyte degeneration/disorganization, Kupffer cell hypertrophy/hyperplasia and pigment, and perivascular mixed cell infiltrates. Serum chemistry and histopathology findings were observed in the 4-week toxicity study at $\geq 56 \mu\text{M}\cdot\text{hr}$ and $180 \mu\text{M}\cdot\text{hr}$, respectively, and were considered monitorable with liver function tests (see Section 1.3.2.6). The hepatotoxicity findings in dogs were associated with moribundity in two high-dose animals. The NOAEL for these findings was considered to be 10 mg/kg ($36 \mu\text{M}\cdot\text{hr}$) in dogs, the most sensitive species, given the absence of GDC-0853-related hepatotoxicity at this dose when administered for 9 months. These findings were fully reversible and considered monitorable by changes in plasma transaminases and bilirubin that occurred at doses lower than those producing histopathology findings. No adverse liver findings were observed in the chronic toxicity studies in rats ($\leq 104 \mu\text{M}\cdot\text{hr}$) and dogs ($\leq 36 \mu\text{M}\cdot\text{hr}$). See Section 4 of the GDC-0853 Investigator's Brochure for further details.
- Fetal malformations were observed in rats (i.e., cleft palate observed at $627 \mu\text{M}\cdot\text{hr}$) and rabbits (i.e., domed-shaped heads with enlarged lateral/third ventricles at $\geq 10.6 \mu\text{M}\cdot\text{hr}$). Thus, highly effective contraception will be mandatory for trial participation, and pregnancy monitoring will be performed at least monthly in Study GA30044.
- Pancreatic findings observed in rats administered GDC-0853, and other BTK inhibitors, were considered to be an on-target, species-specific effect, supported by a number of investigative studies (see the GDC-0853 Investigator's Brochure for details).

1.3.2 Potential Risks for Clinical Toxicities

GDC-0853 is in early clinical development and patient exposure is limited, so the safety profile in patients with SLE is unknown. However, there are several potential risks on the basis of the expected mechanism of action of GDC-0853, published literature for similar molecules, and nonclinical and clinical studies with GDC-0853. Several measures will be taken to ensure the safety of patients participating in this study based on these potential risks (see Section 5.1 for details). In addition, guidelines for the management of study treatment in patients who experience specific adverse events have been established (see Section 5.1.2). Eligibility criteria in this study have been designed to exclude patients at higher risk for potential toxicities (see Section 4.1).

1.3.2.1 Infections

GDC-0853 is a targeted immunomodulator, and the degree to which GDC-0853 antagonism of BTK signaling may suppress immune activity is unknown. Patients participating in this study may be at risk for infections, including opportunistic infections. Therefore, the eligibility criteria are intended to protect patient safety and exclude patients that may be at a particularly increased risk of infection, including those patients with marked baseline lymphopenia. Total Ig concentrations will also be measured regularly throughout the study. During this study, any serious infection, any infection requiring IV antimicrobials, or any opportunistic infection will be considered an adverse event of special interest (AESI) and will require expedited reporting to the Sponsor (see Section 5.4.2).

1.3.2.2 Vaccinations

The effect of GDC-0853 upon the efficacy of vaccinations is unknown. It is recommended that appropriate vaccinations per European League Against Rheumatism (EULAR) recommendations ([van Assen et al. 2011](#)) or local guidelines be up to date before study participation. However, as a safety measure, patients will be excluded from study participation and will not be dosed with GDC-0853 if they have been vaccinated with live, attenuated vaccines (e.g., the intranasal live attenuated influenza vaccines, Bacillus Calmette-Guérin virus, and varicella) within 6 weeks before planned dosing in Study GA30044.

1.3.2.3 Bleeding

BTK is expressed in platelets and is involved in platelet function via GPVI/Collagen receptor signaling and GP1b receptor signaling. Platelets from patients with XLA demonstrate decreased activation in response to submaximal collagen stimulation but normal response to thrombin. However, clinically, there is no reported bleeding propensity in XLA patients ([Howard et al. 2006](#)). In the GDC-0853 clinical study involving patients with cancer, 2 patients experienced Grade ≥ 3 GI bleeding. These events were not dose related and occurred in patients on NSAIDs/acetylsalicylic acid with a history of gastroesophageal or peptic ulcer disease.

It is unknown if GDC-0853 will increase the risk of bleeding in SLE patients receiving antiplatelet or anticoagulant therapies. Therefore, the eligibility criteria will exclude patients at highest risk for GI bleeding. Patients at high risk for NSAID-related GI injury are advised to follow local or recognized guidelines, including concomitant use of proton pump inhibitors (PPIs), if indicated. Any bleeding event of Grade 2 or above is considered an AESI with expedited reporting requirements to the Sponsor (see Section 5.4.2).

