4.1.2 Exclusion Criteria

Patients who meet any of the following criteria will be excluded from study entry:

- Met protocol-defined treatment-stopping criteria during Study GA30044
- An adverse event in Study GA30044 that required permanent discontinuation of study drug
- During Study GA30044, treatment with any therapy that is prohibited in this study (see Section [4.3.2](#))
- In the opinion of the investigator, any new (since initially enrolling in the Phase II Study GA30044), significant, uncontrolled comorbidity or new clinical manifestation (related to SLE or not) that 1) requires medications not allowed in this protocol (see Section [4.3.2](#)) or 2) could put the patient at undue risk from a safety perspective

If the Principal Investigator has questions related to exclusion, he or she should consult the Medical Monitor.

- Pregnant or breastfeeding, or intending to become pregnant during the study or within 60 days after the last dose of study drug
- Any uncontrolled or clinically significant laboratory abnormality that would affect safety, interpretation of study data, or the patient's participation in the study in the opinion of the investigator in consultation with the Medical Monitor
- Any major episode of infection requiring hospitalization or treatment with IV antibiotics within the last 4 weeks of Study GA30044
- Evidence of active, latent, or inadequately treated infection with *Mycobacterium tuberculosis* (TB) as defined as follows:
 - A positive QuantiFERON[®]-TB Gold (QFT) or T-SPOT[®] TB test or a Mantoux purified protein derivative (PPD) skin test (performed per Centers for Disease

Control and Prevention [CDC] guidelines using 5 tuberculin units per 0.1 mL) result of ≥ 5 mm of induration, performed at the Week 44 visit of Study GA30044 or later, prior to entry into Study GA30066

- Patients with a history of bacillus Calmette-Guérin vaccination should be screened using the QFT test only.
- A positive QFT test should be considered a positive diagnostic TB test.
- If initial QFT is indeterminate, perform a confirmatory test with either QFT or T-SPOT. The Principal Investigator may consult with the Medical Monitor to discuss selection of confirmatory test based on the patient's disease status and baseline immunosuppression.
- An indeterminate QFT test followed by a negative QFT or negative T-SPOT test should be considered a negative diagnostic TB test.

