- An indeterminate QFT test followed by an indeterminate QFT test or borderline or positive T-SPOT test should be considered a positive diagnostic TB test.
- Patients who experienced a de novo or reactivated serious viral infection, such as hepatitis B virus or hepatitis C virus (HCV) during Study GA30044
 - Positive hepatitis B surface antigen (HBsAg) or hepatitis C serology (regardless of treatment status) or positive hepatitis B core antibody (HBcAb) (tested at Week 44 of Study GA30044 or later, prior to entry into Study GA30066) are exclusionary.
- Patients who developed a malignancy (with the exception of non-serious local and resectable basal or squamous cell carcinoma of the skin) during the Phase II Study GA30044
- 12-lead ECG at the Week 48 visit of Study GA30044 that demonstrates clinically relevant abnormalities that may affect patient safety or interpretation of study results, including the following:
 - QTcF > 440 msec demonstrated by at least two ECGs > 30 minutes apart
- Current treatment with medications that are well known to prolong the QT interval at doses that have a clinically meaningful effect on QT, as determined by the investigator
 - The investigator may contact the Sponsor for confirmation if needed. The investigator may reference the CredibleMeds[®] Web site:
<https://www.crediblemeds.org/pdftemp/pdf/CompositeList.pdf>.
- Estimated glomerular-filtration rate (based on the 4-variable Modification of Diet in Renal Disease equation) < 30 mL/min or on chronic renal replacement therapy
- Laboratory values from the Week 44 visit of Study GA30044 (which may be repeated once at a later unscheduled visit, if necessary) that meet the following criteria:
 - AST or ALT $> 1.5 \times$ ULN (unless due to known autoimmune hepatitis)
 - Total bilirubin > 1.2 ULN

- Amylase or lipase $> 2 \times \text{ULN}$
- Hemoglobin $< 7 \text{ g/dL}$
- ANC $< 1.5 \times 10^9/\text{L}$
- Absolute lymphocyte count (ALC) $< 0.5 \times 10^9/\text{L}$
- Platelet count $< 50,000/\mu\text{L}$

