5.1.1.3 Bleeding

No decrease in platelets, changes in coagulation parameters (e.g., PT/PTT), or bleeding events were observed in nonclinical studies with GDC-0853. Bleeding events, including non-serious CTCAE Grade 1 bruising and serious Grade ≥ 3 GI bleeding, have been reported in patients with hematological malignancies treated with GDC-0853 in Study GO29089. The GI bleeding events have not been dose related, and the events occurred in patients who were taking concomitant NSAIDs/acetylsalicylic acid and who had a history of gastroesophageal or peptic ulcer disease. The impact of BTK inhibition as a potential risk factor for bleeding is unknown. BTK is expressed in platelets and is involved in platelet function via GPVI/collagen–receptor signaling and GP1b–receptor signaling. Platelets from patients with XLA, a genetic deficiency of BTK, demonstrate decreased activation in response to submaximal collagen stimulation but normal response to thrombin; clinically, there is no reported bleeding propensity of patients with XLA ([Howard et al. 2006](#)).

Bruising or bleeding events related to GDC-0853 have not been reported in healthy subjects.

It is unknown if GDC-0853 will increase the risk of bleeding in patients, especially in those patients receiving antiplatelet or anticoagulant therapies. As a precautionary safety measure, patients will be excluded from participation in the blinded Study GA30044 if they have a need for any of the following:

- Systemic anticoagulation with warfarin or other oral or injectable anti-coagulants or anti-platelet agents (other than NSAIDs, aspirin, and other salicylates)
- Any history of hospitalizations or transfusion for a GI bleed
- Any history of a hemorrhagic cerebrovascular accident
- Any history of spontaneous intracranial hemorrhage
- Traumatic intracranial hemorrhage within 10 years prior to the study
- Known bleeding diathesis

Patients should be advised to seek immediate medical attention if they develop signs and symptoms suggestive of clinically significant bleeding.

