5.2.3 Adverse Events of Special Interest (Immediately Reportable to the Sponsor)

AESIs are required to be reported by the investigator to the Sponsor immediately (i.e., no more than 24 hours after learning of the event; see Section 5.4.2 for reporting instructions). AESIs for this study include the following:

AESIs for GDC-0853

- Any serious infection, any infections requiring IV antimicrobials and any opportunistic infections
- Any bleeding event Grade 2 or above
- All malignancies
- A laboratory result of Grade ≥ 3 (i.e., $> 5 \times \text{ULN}$) AST or ALT elevation

AESIs for General Drug Development

- Cases of potential drug-induced liver injury that include an elevated ALT or AST in combination with either an elevated bilirubin or clinical jaundice, as defined by Hy's Law (see Section 5.3.5.6)
- Suspected transmission of an infectious agent by the study drug, as defined below:
Any organism, virus, or infectious particle (e.g., prion protein transmitting transmissible spongiform encephalopathy), pathogenic or non-pathogenic, is considered an infectious agent. A transmission of an infectious agent may be suspected from clinical symptoms or laboratory findings that indicate an infection in a patient exposed to a medicinal product. This term applies only when a contamination of the study drug is suspected.

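### Section 1.3.2.3 says eligibility excludes patients at highest GI-bleeding risk, but no named entry rule covers a bleed during GA30044 and the parent study's antiplatelet bar is not carried over

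*Combined protocol and SAP*

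**What the plan says.** Section 1.3.2.3 notes that the effect of GDC-0853 on bleeding in SLE patients taking antiplatelet or anticoagulant drugs is unknown, and concludes: "Therefore, the eligibility criteria will exclude patients at highest risk for GI bleeding". The parent Section 1.3.2 makes the general statement: "Eligibility criteria in this study have been designed to exclude patients at higher risk for potential toxicities (see Section 4.1").

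The specific bleeding criteria are in Section 5.1.1.3, where they belong to the parent study: "patients will be excluded from participation in the blinded Study GA30044 if they have a need for any of the following". Six items follow. One is "Any history of hospitalizations or transfusion for a GI bleed". Another is "Systemic anticoagulation with warfarin or other oral or injectable anti-coagulants or anti-platelet agents (other than NSAIDs, aspirin, and other salicylates"). The other four are hemorrhagic stroke, spontaneous intracranial hemorrhage, recent traumatic intracranial hemorrhage and a known bleeding diathesis.

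Sections 4.1.1 and 4.1.2, the entry criteria of this extension, contain no criterion that mentions bleeding. Section 4.3.2 prohibits heparins and other injectable anticoagulants, and oral anticoagulants. It lists no antiplatelet agent. Section 5.2.3 makes "Any bleeding event Grade 2 or above" an adverse event of special interest (AESI).

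**The concern.** The extension enrols patients 48 weeks after they were screened for bleeding risk. A history criterion applied at parent entry cannot see what happened afterwards. A GI bleed that led to hospitalization before GA30044 would have barred the patient from the parent study. The same bleed during GA30044 meets no named rule at entry to the extension.

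Some of these patients were on placebo, because Section 1.3 describes a placebo-controlled parent study. They would be starting 200 mg BID for the first time with a recent major bleed, on a drug whose effect on bleeding the protocol calls unknown. Section 1.3.2.3 also reports two patients with Grade 3 or higher GI bleeding on GDC-0853 in the oncology study, both on NSAIDs or acetylsalicylic acid and with a relevant gastrointestinal history.

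The antiplatelet omission matters for the same reason. The rationale in 1.3.2.3 names antiplatelet therapy alongside anticoagulants, yet only anticoagulants are prohibited here.

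**Working it through.** No calculation applies, and the plan gives no figure to reproduce. The check compares the sections and then traces one patient through the entry rules.

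**Step 1. Parent bleeding items against the extension's rules.**

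| Section 5.1.1.3 (GA30044 entry) | Named in 4.1.2? | Reached through 4.3.2? |
|---|---|---|
| GI bleed with hospitalization or transfusion | No | No |
| Hemorrhagic stroke | No | No |
| Spontaneous intracranial hemorrhage | No | No |
| Traumatic intracranial hemorrhage | No | No |
| Bleeding diathesis | No | No |
| Need for anticoagulants | No | Yes: 2 of 14 items |
| Need for antiplatelet agents | No | No: 0 of 14 items |

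The sixth parent item is split into two rows because its halves fare differently. Section 4.1.2 excludes anyone treated during GA30044 with a therapy that 4.3.2 prohibits, so the anticoagulant half is carried into eligibility and the antiplatelet half is not.

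**Step 2. A patient hospitalized for a GI bleed midway through GA30044, who recovered, resumed study drug and completed Week 48.**

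- *Met GA30044 stopping criteria:* cannot be determined, because the parent protocol is not among these documents. As a guide to the sponsor's approach, bleeding is not on the mandatory discontinuation list in Section 4.5.1 of this protocol. Table 3 handles Grade 3 or higher or serious bleeding by withholding drug, with possible resumption after discussion with the Medical Monitor. That the parent study did likewise is an assumption.
- *Adverse event requiring permanent discontinuation:* not met, since drug was resumed.
- *Hemoglobin below 7 g/dL or platelets below 50,000/µL:* read at Week 44 of GA30044, so not met after recovery.
- *Prohibited therapy during GA30044:* not met by the bleed itself.
- *Acceptable safety and tolerability (4.1.1), or a new comorbidity or manifestation carrying undue risk (4.1.2):* could exclude the patient, but only if the investigator so judges.

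So the routes left are investigator judgment and an unseen parent rule.

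**Step 3. A patient who comes to need a non-aspirin antiplatelet agent.** Section 4.3.1 discourages added drugs for non-SLE conditions but permits them when needed. Section 4.5.1 requires stopping study drug for treatments not specifically permitted, with a reference to 4.3.1 and to Medical Monitor approval. Read together, these allow the agent when it is required and approved. Appendices 7 and 15 agree with that reading: ticagrelor appears only in the row for CYP3A substrates to be used with caution. The extension therefore allows, with approval, a class that barred entry to the parent study.

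**The case against.** The strongest reply is that 1.3.2.3 is largely fulfilled. Every patient passed the GA30044 criteria, so bleeding history before that point was screened for all. Section 1.3.2 describes inherited parent criteria as eligibility elsewhere too: the vaccine rule in 1.3.2.2 is tied to dosing in GA30044, and the 10-year cancer rule in 1.3.2.9 has no counterpart in 4.1.2. Leaving later events to the investigator is ordinary in a rollover study. Grade 2 or higher bleeds are also reported within 24 hours, and the monitoring committees review safety regularly. All of this stands and limits the point to events after parent entry. It does not supply a rule for those events.

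Two stronger readings are tempting, and the documents support neither.

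- *A reader might infer that bleeding is the one GDC-0853 AESI class that the entry criteria leave open.* The comparison is uneven. The AST/ALT limit is also a Week 44 value and would miss a recovered elevation. The general infection rule reaches back only a short way: "Any major episode of infection requiring hospitalization or treatment with IV antibiotics within the last 4 weeks of Study GA30044". An earlier serious infection that resolved also passes, unless it was a serious viral infection, which has its own exclusion. Among the four classes, only malignancy is covered across the whole parent study: "Patients who developed a malignancy (with the exception of non-serious local and resectable basal or squamous cell carcinoma of the skin").
- *A reader might infer that 4.3.1 permits a new antiplatelet agent while 4.5.1 forbids it.* The sentence in 4.5.1 refers to 4.3.1 and adds Medical Monitor approval. That is supervised permission, not a contradiction.

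It is also fair to say that excluding any qualifying bleed since parent entry is stricter than the four-week infection window, and stricter than Table 3, under which a patient who bleeds in the extension may resume. The stricter rule is justified because it matches the sponsor's own history-based parent criteria, and because entry may be a first exposure to drug.

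**Conclusion.** The point holds in a limited form. Section 1.3.2.3 claims an eligibility safeguard that Section 4.1 does not contain for bleeds arising during the 48 weeks of GA30044, and 4.3.2 drops the antiplatelet half of a parent exclusion. The antiplatelet gap also runs through up to 48 weeks of extension treatment.

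The conclusion about text needs no assumption. How many patients it affects depends on three things not in the documents: the parent stopping criteria, the parent prohibited-therapy list, and the rate of major bleeding. The severe or Grade 3 events that Section 1.2.3 reports from the RA and SLE trials include no bleed, so the number may be small. No count out of the roughly 240 eligible patients can be given.

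This is a participant-safety correction. A reader might infer that it biases the primary result, but the safety analysis in Section 6.4 includes everyone who receives at least one dose, so it does not.

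**What to change.** 1. Add to Section 4.1.2 an exclusion for any of the following since entry to GA30044: a GI bleed requiring hospitalization or transfusion, a hemorrhagic stroke or intracranial hemorrhage, or a newly identified bleeding diathesis. This matches the parent criteria and brings them up to date.
2. Add to Section 4.3.2 antiplatelet agents other than NSAIDs, aspirin (up to the 325 mg/day already allowed in Section 4.3.1.5) and other salicylates. Section 3.1 and Section 4.5.1 then settle on-study use, since prohibited medication requires stopping GDC-0853.
3. Cross-reference the new prohibition at the ticagrelor entry in Appendices 7 and 15. Section 4.3.2.2 already makes the caution list subject to 4.3.2, so this is for clarity only.

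Table 3 can stay as it is. The cost is a short amendment with no new data collection. A few patients become ineligible. Because 4.1.2 excludes anyone who took a prohibited therapy during GA30044, these include patients whose antiplatelet course in that study is already finished. Others would have to stop study drug if they come to need an antiplatelet agent.
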